15 DATA HANDLING AND RECORD KEEPING

The investigators are responsible for ensuring the accuracy, completeness, legibility, and timeliness of the data reported. All source documents should be completed in a neat, legible manner to ensure accurate interpretation of data. The investigators will maintain adequate case histories of study participants, including accurate CRFs, and source documentation. The Data Management Plan is detailed in Appendix D.

Only study personnel (i.e., GPI, SPI, Co-Investigator's, RCs, and CC personnel) and clinical site monitors will have access to the study data elements in the study database as described in Section 15.3 Types of Data. Study personnel will include those who are on the approved IRB study protocol. All study personnel will have completed the required training elements for human subjects research certification.

15.1 Data Management Responsibilities

Data collection and accurate documentation are the responsibility of the study staff under the supervision of the investigator. All source documents must be reviewed by the study team and data entry staff, who will ensure that they are accurate and complete. Unanticipated problems must be reviewed by the investigator or designee.

Staff at the RAS will collect paper CRFs from practitioners, perform a QC review and send the forms to the CC for data entry into the online web system. For the paper CRFs that are to be used as source documents (see Section 12), the RAS staff will ensure the signatures on the forms are completed and the copies are securely stored at practitioners' sites. The RAS staff and the CC will ensure the data are entered and the discrepancies generated by the system are resolved in a timely fashion based on study requirements. The RAS staff will work with practitioners and/or patients to clarify any data issues and maintain a tracking log for the data changes. To aid the data collection and data entry activities, the CC will provide paper CRF completion and electronic data entry guidelines. All of the paper CRFs will be sent to the CC for data entry by CC staff.

15.2 Data Capture Methods

Study-specific paper CRFs will be developed to include fields for all data elements required for participant assessments. A secure webpage will also be developed and used to capture data from an online practitioner questionnaire as well as patient follow-up assessments for those who choose to complete them online. A Web-based data collection system will ensure that all required data (paper and online) are collected in the study database. As most fields will require a categorical response and some fields will ask for a numeric response, the data field in the database will be programmed to allow only certain values and ranges so that data entered from the web system can be validated and data errors be corrected. Reports and tools will be developed to help monitor the visit and data activities. The reports with the summary of the data completion at enrollment and follow-up by the practitioners and patients will be made available on the network web site.

After the paper data collection has been completed for a participant at enrollment and at each follow-up assessment, the study materials for the participant will be placed in a secure location. The participant log will be consulted to obtain the name of the patient corresponding to the study ID number printed on the CRF. Questions about the data will be resolved by conferring with the staff member(s) or the patient who completed the CRF. After the dentist signs the CRF, the designated staff member will transmit the data to the RCs. The trained staff at the RAS will review the data and send it to the CC for data entry into the study database. RAS staff members will respond to data queries generated by the data capture system and will have access to support staff at the CC if they need assistance with data processing.

Patients will be responsible for the submission of the 1-, 4-, and 8-week follow-up assessments within the study assessment windows. Reminders and other tools will be used to encourage timely submission of these assessments however it is known that some patients may not comply. Follow-up assessments received outside of the study specified windows will be accepted; though this data may not be included in the analysis, it would still be of interest to the study team.

15.3 Types of Data

Data for the present study consist of the following:

- Practitioner-level data from the National Dental PBRN enrollment questionnaire and the study online practitioner questionnaire,
- Patient characteristics data from baseline questionnaire,
- Patient-, pain-, treatment compliance-, and satisfaction follow-up assessments, and
- Unanticipated problems data (collected in the main study database).

15.4 Schedule and Content of Reports

Reports to monitor enrollment will be produced every 2 weeks during the 4-6-month participant enrollment period, until enrollment targets are attained and enrollment is closed. These reports will contain a section for accrual information in aggregate, with information on accrual of participants according to key characteristics (symptomatic vs. asymptomatic) cross-tabulated with treatment recommendation (Yes vs. No). These reports will also contain separate sections for each region, with information regarding participant accrual by site.

Reports to the DSMB will be produced at least annually, and may be produced more frequently at the request of the DSMB. As noted in Section 9 Study Oversight, most data elements for inclusion in the DSMB reports will be clearly defined at the organizational meeting of the DSMB. In addition to enrollment and retention reporting, the DSMB study progress reports will contain safety data as well as frequencies and

descriptive statistics for primary outcome variables and key variables. The identification of key variables will be determined by the SPI and other study team members.

Reports to assess study retention will be produced every 2 weeks. These reports will provide ongoing monitoring of participant retention. Retention data will be closely monitored, and futility analyses will be performed as needed. In addition, a report will be produced for each individual practice that includes the practice's attrition rate and a comparison to the overall attrition rate for the study. These reports will be made available to the practitioners. For patients who are lost to follow-up, reports to assess reasons for loss will be produced after data has been obtained following the data collection period for each study follow-up assessment.

The procedure for locking the database prior to final analysis will be detailed in Section 13 of the study Data Management Plan, in accordance with the Westat CCs *SOP DSD-001: Development of a Data Management Plan* (see Appendix D) and *SOP DSD-405: Data Lock*. Briefly, the data will be locked and the final SAS datasets will be generated at the end of the study. Prior to locking the database, the Clinical Data Manager (CDM) or designee will ensure all data is complete and clean. Then, the CDM will obtain approval from the Project Manager to proceed with the data lock. The CDM will then direct the Database Development Manager to lock the database. The date and time of database lock will be documented. All team members will receive written notification from the CDM or designee when the database lock is complete.

No masking or coding is anticipated for this study.

15.5 Study Records Retention

Study records will be maintained for at least three years from the date that the grant federal financial report (FFR) is submitted to the National Institutes of Health (NIH) or longer as dictated by local IRB or state laws/regulations.

As outlined by IRB regulations, data will be destroyed in an appropriate and safe way after three years.

The file connecting subjects' names with their unique identification number will be kept in a password-protected file by the CC and on the GPI's computer for a minimum of three years, in accordance with IRB regulations, before being securely erased.

15.6 Protocol Deviations

A protocol deviation (PD) is any noncompliance with the clinical study protocol or good clinical practice principles. The noncompliance may be on the part of the subject, the investigator, or study staff. As a result of deviations, corrective actions are to be developed by the study staff and implemented promptly. All deviations from the protocol must be addressed in study subject source documents and promptly reported to NIDCR and the local IRB, according to their requirements.

Any PD that is reportable to an IRB must also be reported to NIDCR. NIDCR defers to the IRB for reporting time-frame requirements. Once a PD has been reported to an IRB, action must be taken to report the deviation to NIDCR. If the IRB overseeing the study protocol requires annual reporting of PDs to their IRB, that reporting frequency is acceptable to NIDCR. At the time of each DSMB review, all previously unreported PDs must be reported to the DSMB independent of when they are reported to IRBs.

16 PUBLICATION POLICY

This study will comply with the [NIH Public Access Policy](#), which ensures that the public has access to the published results of NIH-funded research. It requires scientists to submit final peer-reviewed journal manuscripts that arise from NIH funds to the digital archive [PubMed Central](#) upon acceptance for publication.

All study personnel are required to read in its entirety and agree to abide by the network's "Data Analysis, Publications, and Presentations Policies" document. The current version of this policy is always kept at the network's public web site at <http://nationaldentalpbrn.org/publication.php>.

Appendix A. Schedule of Events

Appendix B. Subject Retention Plan

Appendix C. Quality Management Plan

Appendix D. Data Management Plan

Appendix A: Schedule of Events

Procedures	Baseline Study Visit				2 nd -Line Treatment Visit				3 rd -Line Treatment Visit				Premature Discontinuation/ Withdrawal
	Enrollment/Baseline (Day 0)	1 Wk Follow-up (Day 7, -6 to +6)	4 Wk Follow-up (Day 28, -6 to +6)	8 Wk Follow-up (Day 56, -6 to +6)	2 nd -Line Treatment	1 Wk Follow-up (Day 7, -6 to +6)	4 Wk Follow-up (Day 28, -6 to +6)	8 Wk Follow-up (Day 56, -6 to +6)	3 rd -Line Treatment	1 Wk Follow-up (Day 7, -6 to +6)	4 Wk Follow-up (Day 28, -6 to +6)	8 Wk Follow-up (Day 56, -6 to +6)	
Obtain Informed Consent	X												
Assessment of Eligibility Criteria	X												
Review of Medical/Dental History	X												
Obtain/confirm contact information and preferred method of contact	X				X				X				
Oral Examination	X				X				X				
Patient Demographics (in office)	X												
Pain Assessment (in office)	X				X				X				X ¹
Treatment prescribed and/or performed	X				X				X				
Follow-up Pain Assessment (online or mail)		X	X	X		X	X	X		X	X	X	
Compliance with treatment		X	X	X		X	X	X		X	X	X	X ¹
Satisfaction with treatment				X				X				X	X ¹

¹ Obtain only if withdrawal occurs during an in-office visit and consent is not withdrawn.

- 3) Make contact with study subjects prior to the follow-up assessment due date. The subject's preferred method of contact (e.g., text message, email, or telephone) will be ascertained at the baseline appointment.
- 4) Prior PBRN studies have shown that personal relationships, both between the subjects and offices, and the offices and the RCs promoted successful execution of PBRN studies. It will be important to study subjects to receive a message from the RCs or CC regarding a reminder for a study follow-up assessment.
- 5) Experience from the prior network has also shown that it is important to relieve burden on the practices. As such, the National Dental PBRN will request IRB approval for the RCs and for the CC to receive the subject contact information and the contact information of one person who does not live in the same household as the subject, to assist the RCs and the CC in their follow-up with the study subjects post baseline. The regions will have some latitude in determining the best means for maintaining contact with the study subjects and ensuring their ongoing participation.
- 6) Number of Subjects per Practitioner Considerations:
Ask practitioners to enroll at least approximately 10-14 subjects during the enrollment period.
- 7) Given the above design features, subjects should not be "lost". However, if a subject moves and contact is lost, the CC has extensive experience with using tracing resources such as National Change of Address services, motor vehicle departments, and LexisNexis databases. In those cases, the CC may implement those tracking procedures.
- 8) The process for contacting subjects for follow-up assessments will be attempted by the RC and the CC. If unsuccessful, the CC may initiate tracking procedures to identify updated subject contact information. Initiating tracking procedures promptly when there is no subject response to contact attempts will minimize missed follow-up assessments and also minimize loss to follow-up.

Methods to Minimize “Missing Data”

- 1) Put all participating practitioners on the same study schedule. Have an enrollment phase, then a break, then another specific follow-up phase of a couple of weeks and continue this cycle over the course of the study. Offices in general do a good job enrolling subjects because they are focused on the study every day during the enrollment period. However, it is more challenging to remember to perform study procedures when the enrollment phase is over and they may only have a study subject in the office once every couple of weeks. Within the enrollment period, the office enrolls eligible subjects, with a goal of 10-14 subjects. Subjects will be required to complete their follow-up assessments at 1-, 4- and 8-weeks post baseline visit. Prior to each assessment interval, subjects will be contacted via text message, email or phone to remind them about the upcoming assessment. The method of the preferred contact will be ascertained at the baseline visit. The CC and RCs will be responsible for making these reminders. Subjects will return the study assessments by completing them on the designated webpage or mailing them by the US post office to the designated RC.
- 2) Ask participating offices to develop a system to flag records of subjects in their practices who are participating as subjects in the study, as well as to flag study subjects in the office schedule. In this way, study personnel will be alerted to the fact that the subject is at the office, and can ensure that data collection takes place if indicated. Flagging the subject in the schedule will help to ensure that subjects are not inadvertently scheduled when the practitioner will not be in the office. In the same way, if a subject’s record is requested by another office, study personnel can inform the RC and attempts made to maintain the subject in the study.
- 3) For subjects returning with symptoms, ask the practitioners to set aside specific time for follow-up in the office as necessary or appropriate.
- 4) Emphasize to practitioners as part of their initial study packages that the dentist has to be the motivational director of the study, especially regarding explaining to the study subjects that follow-up assessments are essential components of the study and make sure that the staff understands that the office is committed to taking the study on and seeing it through to completion.

Methods to Minimize “Refused”

- 1) The method described under Methods to Minimize “Lost”, first point, will also help reduce the number of subjects who refuse to continue participating. At enrollment, subjects are informed that they are agreeing/consenting to participate in a longitudinal study. Subjects who enroll are required to state a willingness to participate throughout the study.

- 2) The method described under Methods to Minimize “Lost”, third point (making contact prior the follow-up assessment interval), should also help reduce refusals. Additionally, follow-up involvement will be kept as light and convenient for the subject as possible.

Methods to Minimize “Unable”

- 1) There are several scenarios in which a subject stops seeing the original/enrolling practitioner:
 - a. Subject does not move, but:
 - i. Subject changes dentists- in same practice
 - ii. Subject changes dentists- in different practice
 - iii. Subject stops seeing any dentist
 - b. Subject moves
 - i. Subject sees new dentist
 - ii. Subject stops seeing any dentist
 - c. Dentist retires or dies
 - d. Dentist moves
 - e. Dentist refuses to continue participating (shouldn't happen)
- 2) The operational impact of all of the above scenarios can be summarized by two scenarios:
 - a. Subject has a new dentist (not a National Dental PBRN member)
 - b. Subject stops seeing any dentist
- 3) Locating the subject should not be a problem (see Methods to Minimize “Lost”), and having the subject agree to continue participating should not be a problem (see Methods to Minimize “Refused”).
- 4) The main operational issue is: How to get study follow-up assessment information from subjects seeing a non-National Dental PBRN dentist or not seeing any dentist.
 - a. Actively recruit the new dentist into the Network so the subject can continue to be followed by the new dentist.
 - b. Request permission from the new office to complete a chart abstraction to obtain data.

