4 STUDY DESIGN

- This is a prospective, multicenter cohort study of DH. For the study, practitioners and patients will be recruited from six National Dental PBRN regions across the US.
- The study population will consist of adult dental patients (19 years old or older) who have DH and the practitioners who provide treatment for DH. Dental practitioners are included in the population being studied because diagnostic modalities as well as treatment recommendations and approaches for DH are being studied. It is anticipated that approximately 180 dentist practitioners across the US will be enrolled (approximately 30 practitioners per National Dental PBRN region). Each dental practitioner will enroll approximately 14 study patients with an enrollment aim of 2,520 adult patients.
- The prospective, observational, multicenter design of the study will allow us to construct a picture of how patients with DH are cared for in dental offices across the US and how practitioner-, practice-, patient- and tooth- characteristics relate to the selected treatment(s) and approach(es) to care. The proposed study will provide further understanding about DH management based on a sample of US dental providers enrolled in the network and may provide data to establish guidelines for treating DH. The usual and customary treatment of DH that dentists apply in their practice will be assessed.
- After enrolling in the study and providing consent, practitioners will receive a link to a secure webpage and will be asked to complete an online questionnaire before recruiting and enrolling patients to the study.
- To determine if a patient meets the criteria for study inclusion, the patient must first indicate intraoral pain/sensitivity by self-report. Patients with a medical condition that could interfere with reliable pain reporting (e.g., cognitive impairment, dementia), chronic pain condition (fibromyalgia, lower back pain, irritable bowel syndrome, temporo-mandibular joint (TMJ) disorder), and patients who report having taken analgesics more than three times in the past week will be excluded from the study. Next, the practitioner will perform an oral examination to assess other causes of tooth sensitivity such as pulpitis or dental infection. A diagnosis of DH will be made when the practitioner has excluded other etiologies of odontogenic pain.

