5.3.2 Patient Recruitment

We plan to enroll approximately 2,520 patients in an approximate 4-6-month period. Each practitioner will be asked to recruit approximately 14 patients. Recent data from

the Northwest PRECEDENT network have shown that the prevalence of DH among the patients seen by the practitioners enrolled in the previous network was 12.3% (Cunha-Cruz et al., 2013).

Any dental or hygiene visit will be eligible for patient recruitment to the study. A convenience sampling approach will be used to enroll patients in the study with an emphasis upon enrolling the first 14 patients presenting to the dental office who meet the eligibility criteria.

Patients presenting with DH at any dental visit in the dental office will be eligible for the study. Designated office personnel will introduce the study to patients who meet the inclusion criteria when they are seen for a dental appointment. Patients who meet eligibility criteria and show interest in participating in the study will be invited to participate, and a designated person will perform informed consent procedures. It is anticipated that in most instances it will be a dentist who will perform informed consent procedures. Patients will receive \$125 for their participation - \$25 upon completion of the baseline office visit, \$25 upon completion of the follow-up assessment at 1 week, \$25 upon completion of the follow-up assessment at 4 weeks and \$50 upon completion of the study.

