11.1 Sample Size Considerations

The expected sample for the study will include approximately 180 practitioners, each enrolling 14 patients presenting with DH, for a total sample size of approximately 2,520 patients.

Calculations of sample size requirements for the primary objectives addressing estimation of percentages were based on widths of 95% confidence intervals for binomial proportions, adjusted for the effect of clustered sampling, with clusters defined by sampling multiple patients within the same dental practice. Adjustment for clustering was done by calculating effective sample sizes using variance inflation factors for a range of likely values of intracluster correlation (ICC). Power to detect a difference between proportions of dentists using each of the treatment modalities were estimated for chi-square tests, adjusted for the effect of clustered sampling in order to approximate the power of the proposed GEE analysis.

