Present calculations from a suitable range of assumptions to gauge the robustness of the proposed sample size. Most assumptions are not accurate as point estimates.

[figure not shown]
Effective sample sizes were calculated for 180 dentists, 10 to 20 patients per dentist, and values of ICC from 0.00 to 0.05. Expected widths of 95% confidence intervals around a true proportion of 0.50 were calculated for each effective sample size. The value of 0.50 was used as this is the value that yields the maximum variance for a binomial distribution, for a given sample size. Thus, these calculations provide upper bounds for the widths of confidence intervals for each sample size, providing conservative estimates in case ICC is higher than expected. Effective total sample sizes for the different values of ICC and numbers of patients per dentist are presented in the following chart.

[figure not shown]
The expected widths of confidence intervals for the primary estimation aims are presented in the following chart. The first set of expected widths was calculated for the entire sample, to illustrate the total information content of the sample, given each of the sample size choices. These expected widths range from 3.3%, reflecting estimation within $\pm 1.65\%$, for 20 patients per dentist and ICC equal to 0.0, to 5.0%, reflecting estimation within $\pm 2.5\%$, for 10 patients per dentist and ICC equal to 0.05. As seen in the plot, increasing the number of patients per dentist from 10 to roughly 16 provides substantial increases in precision, with smaller gains in precision with increases to 18 or 20 patients per dentist.

Assuming that four main treatment groups occur, then the expected widths of 95% CIs on the percentages of patients in each of these subgroups would range from 13.1% (estimation within $\pm 6.5\%$) for 20 patients per dentist and ICC equal to 0.0 to 22.3% (estimation within $\pm 11.15\%$) for 10 patients per dentist and ICC equal to 0.05. The expected widths of these CIs are shown in the following chart, which presents the same pattern across sample sizes as that for the entire sample.

[figure not shown]

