Precision of estimation of mean change in reported pain scores is shown in the following chart. Four equal-sized subgroups of the total sample were assumed. Widths were calculated for CIs within a single subgroup. Precision is represented as the widths of 95% confidence intervals, based on the Normal distribution, in units of standard deviation of the change scores.

[figure not shown]

Power to detect a medium effect size for difference in VAS score between treatments is approximately 100% for all effective sample sizes that were considered. Differences between group means that would be detectable range from 0.095sd for 20 patients per dentist and ICC equal to 0.0 to 0.160sd for 10 patients per dentist and ICC equal to 0.05. Thus, all configurations that were considered provide substantial power to detect very small effect sizes, yielding confidence that the study will be adequately powered,

even if ICC is larger than those assumed in the power calculations. Power to detect a difference between treatment group means is shown in the following chart.

Given the results of these power calculations and practical considerations, we will recruit 180 dentists, who will each recruit 14 patients, for a total sample size of 2,520 patients. This will provide protection against loss of power due to potential dropout of patients or of dentists, and against finding larger than expected correlation among observations made by the same dentists. If a patient loss to follow-up of 20% were to occur, the study would still include 2,016 patients, which would still provide essentially 100% power to detect a medium effect size, for likely magnitudes of ICC. Similarly, while it is unlikely that practitioner dropout will occur, loss of as many as 10 practitioners would result in a total expected sample size of 2,380 patients, again providing very high power if ICC is of the expected magnitude. The proposed sample size provides substantial protection against the possibilities that ICC might be higher than anticipated or that the effect size might be smaller than anticipated.

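### Section 11.1 understates the confidence interval width at 10 patients per dentist (5.0%, should be 5.6%), and Appendix B's goal of 10-14 per practice conflicts with the planned 14

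*Protocol*

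**What the plan says.** **Enrolment target in the body.** Section 4 states: "Each dental practitioner will enroll approximately 14 study patients with an enrollment aim of 2,520 adult patients". Section 5.3.2 puts the emphasis on "enrolling the first 14 patients presenting to the dental office who meet the eligibility criteria". Section 11.1 opens with "approximately 180 practitioners, each enrolling 14 patients presenting with DH, for a total sample size of approximately 2,520 patients" and concludes that "we will recruit 180 dentists, who will each recruit 14 patients, for a total sample size of 2,520 patients". The summary and section 5.1 give the same numbers.

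**Enrolment target in Appendix B.** The Subject Retention Plan gives a different figure twice. Under the methods to minimize lost subjects, item 6 reads "Ask practitioners to enroll at least approximately 10-14 subjects during the enrollment period". Under the methods to minimize missing data, item 1 describes each office enrolling eligible subjects "with a goal of 10-14 subjects".

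**Precision.** Section 11.1 evaluates 180 dentists, 10 to 20 patients per dentist and ICC from 0.00 to 0.05. For the whole sample it gives widths from 3.3% (20 per dentist, ICC 0) to 5.0%, or ±2.5%, "for 10 patients per dentist and ICC equal to 0.05". For the same two configurations it gives detectable differences in pain score of 0.095 and 0.160 SD.

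**The concern.** There are two separate problems, and both concern the 10-per-dentist case.

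First, the 5.0% is offered as the widest whole-sample interval among the configurations studied. Section 11 describes the study as driven by estimation, and section 11.1 bases precision for the primary objective on interval widths. An error in the upper limit of that range is therefore an error in the main justification for the sample size.

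Second, the protocol gives two per-practice targets and nothing reconciles them. A practice that stops at 10 has met the Appendix B goal but is 4 patients short of the section 11.1 plan. Replacement under section 5.4.2 covers only patients who withdraw or discontinue. The two-weekly accrual reports in section 15.4 would show a low count, but no stated rule says which target applies or how a shortfall is made up.

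At stake are the planned total, the margin for dropout and some precision.

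**Working it through.** **Inputs, all from section 11.1 unless noted:** k = 180 dentists; m = 14 patients per dentist (planned) or 10 (lower end of Appendix B); ICC 0 to 0.05; true proportion 0.50; 95% confidence; 20% loss to follow-up; Type I error 5% (two-sided assumed, since sidedness is not stated); power 80%; effect 0.5 SD between two equal groups.

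**Formulas**
- Effective n = k·m / (1 + (m − 1)·ICC)
- 95% CI width = 2 × 1.96 × √(0.25/n) = 1.96/√n
- Detectable difference in SD = (1.96 + 0.84) × √(4/n)

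**1. Reproduce the plan's figures**
- Total: 180 × 14 = 2,520. After 20% loss: 2,520 × 0.8 = 2,016. With 10 practitioners lost: 170 × 14 = 2,380. All agree with the protocol.
- Narrowest width, 20 per dentist, ICC 0: n = 3,600; 1.96/√3,600 = 3.27%. Stated 3.3%: agrees.
- Detectable difference, 20 per dentist, ICC 0: 0.093 SD. Stated 0.095: agrees closely.
- Detectable difference, 10 per dentist, ICC 0.05: n = 1,800/1.45 = 1,241, giving 0.159 SD. Stated 0.160: agrees.
- Widest width, 10 per dentist, ICC 0.05: 1.96/√1,241 = 5.56%, or ±2.8%. Stated 5.0%, ±2.5%: **does not agree**.

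**2. Is the 5.0% or the method at fault?**
- The protocol's 0.160 SD fits an effective n of 1,241. At an effective n of 1,527 it would be 0.143 SD.
- The four-group widths in section 11.1 run from 13.1% to 22.3%, and the text says they follow the same pattern as the whole sample. Their ratio is 22.3/13.1 = 1.70. The whole-sample ratio as stated is 5.0/3.3 = 1.52; with the recomputed values it is 5.56/3.27 = 1.70. (Only the ratio is used here; the absolute level of the four-group widths is a separate question.)
- Both checks point to the single figure of 5.0% as the error.
- At ICC 0.05, 5.0% is the width for 14 per dentist: 2,520/1.65 = 1,527; 1.96/√1,527 = 5.02%. It is also the width for 10 per dentist at ICC 0.02: 1,800/1.18 = 1,525; 5.02%. The numerical match does not show how the slip arose.
- At 10 per dentist the stated 5.0% is exceeded once n falls below (1.96/0.05)² = 1,537, that is once ICC passes (1,800/1,537 − 1)/9 ≈ 0.019, inside the range studied.

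**3. What 10 instead of 14 per practice would cost (worst case, all 180 practices)**

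| | 14 per dentist | 10 per dentist |
|---|---|---|
| Enrolled | 2,520 | 1,800 (720 fewer, −28.6%) |
| After 20% loss | 2,016 | 1,440 |
| Effective n, ICC 0.05 | 1,527 | 1,241 |
| CI width, ICC 0 | 3.90% | 4.62% |
| CI width, ICC 0.05 | 5.02% | 5.56% |
| Detectable difference, ICC 0 | 0.112 SD | 0.132 SD |
| Detectable difference, ICC 0.05 | 0.143 SD | 0.159 SD |
| Power for 0.5 SD | about 100% | about 100% |

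With 1,440 retained (8 per dentist) and ICC 0.05, effective n = 1,440/1.35 = 1,067. The standardized difference is 0.5 × √(1,067/4) = 8.2 against a critical value of 1.96, so power is still about 100%.

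**The case against.** The strongest reply is that little depends on the difference between 10 and 14. Most of it stands.

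- **Ten is inside the range studied.** Section 11.1 finds every configuration from 10 to 20 per dentist well powered and chose 14 partly on practical grounds. A reader might infer that the sample size needs 14, or that the study would be underpowered at 10. The documents do not support that: power for 0.5 SD stays near 100%, and the 0.160 SD limit is itself the 10-per-dentist case and is met.
- **Not every precision claim fails at 10.** The quoted widths and detectable differences describe the 10- and 20-per-dentist extremes, not 14. What is missed at 10 is the head count (2,520 and 2,016) and, at higher ICC, the stated 5.0% limit. The loss to follow-up also bears only on the pain-trajectory objective; section 11.1 expects no withdrawals for the cross-sectional objectives.
- **Appendix B does not govern recruitment.** It is a retention plan; section 5.3 sets recruitment. Even so, section 5.3.3 refers to Appendix B and its item 6 says what to ask of practitioners, so it is current instruction.
- **1,800 is a worst case.** It requires every practice to stop at the bottom of a loosely worded range, while accrual by site is reported every two weeks. The body also mostly says approximately 14.
- **The text does not hide the cost of a lower goal.** Section 11.1 says precision improves appreciably from 10 to about 16 per dentist and gives the larger detectable difference at 10.

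The reply does not remove either error. A figure of 10 is not approximately 14, and the 5.0% is wrong at any recruitment level because it is labelled as the 10-per-dentist value.

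**Conclusion.** Both points hold, at modest size.

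The width in section 11.1 for 10 per dentist at ICC 0.05 should be 5.6% (±2.8%), not 5.0% (±2.5%). This rests only on the protocol's stated method (effective sample size, normal approximation, proportion 0.50) and is supported by two other results in the same section.

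The Appendix B goal of 10-14 contradicts the approximately 14 per practitioner and 2,520 total in the body. If all 180 practices stopped at 10, enrolment would be 1,800, below the 2,016 that section 11.1 counts on after 20% loss and before any loss has occurred. At ICC 0.05 the whole-sample width would go from 5.0% to 5.6%, about 0.27 percentage points on each side. The protection against dropout and a higher ICC, for which 14 was chosen, would be partly used up in advance.

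This is an internal inconsistency and one wrong figure. It is not a flaw in the choice of 14 and not a loss of power. Both should be corrected, because precision is what the study is designed to deliver.

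**What to change.** 1. In section 11.1, change the whole-sample width for 10 patients per dentist at ICC 0.05 from 5.0% (±2.5%) to 5.6% (±2.8%), and check that the accompanying chart shows the corrected value.
2. In Appendix B, change both statements of 10-14 subjects (lost subjects, item 6; missing data, item 1) to approximately 14 patients per practitioner.

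The cost is one corrected figure and two wording changes. The design, the analysis and the planned 2,520 patients are unaffected.
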